6.3 SUBJECT SETS ANALYSED

Section 7.3 of the CTP: Statistical analyses will be based on the following analysis sets:

- *Treated set (TS): The treated set includes all subjects who were treated with at least one dose of trial drug. The treatment assignment will be determined based on the (first) treatment the subjects received. The treated set will be used for safety analyses.*
- *PK parameter analysis set (PKS): This set includes all subjects in the TS who provide at least one primary PK endpoint that was not excluded due to a protocol deviation relevant to the evaluation of PK or due to PK non-evaluability (as specified in the following subsection 'Pharmacokinetics'). Descriptive and model based analyses of PK parameters will be based on the PKS. It is expected that PK data from replaced subjects is not evaluable and thus replaced subjects are not expected to be part of the PKS.*

Plasma concentration data and parameters of a subject will be included in the statistical PK analyses if they are not flagged for exclusion due to a protocol deviation relevant to the evaluation of PK (to be decided no later than in the Report Planning Meeting) or due to PK non-evaluability (as revealed during data analysis, based on the criteria specified below).

Exclusion of a subject 's data will be documented in the CTR.

Relevant protocol deviations may be

- *Incorrect trial medication taken, i.e. the subject received at least one dose of trial medication the subject was not assigned to*
- *Incorrect dose of trial medication taken*
- *Use of restricted medications*

Plasma concentrations and/or parameters of a subject will be considered as non-evaluable, if for example

- *Missing samples/concentration data at important phases of PK disposition curve.*

Plasma concentration data and parameters of a subject which is flagged for exclusion will be reported with its individual values but will not be included in the statistical analyses.

Table 6.3: 1 Subject sets analysed

Class of endpoint	Subject analysis set	
	Treated set	PKS
Analysis of PK endpoints		X
Safety parameters	X	
Demographic/baseline parameters	X	
Important protocol deviations	X	
Disposition	X	

6.5 POOLING OF CENTRE

This section is not applicable, because the study was performed in only one centre.

6.6 HANDLING OF MISSING DATA AND OUTLIERS

Handling of missing data and outliers will be performed as described in the CTP, Section 7.4.

The only exceptions where imputation might be necessary for safety evaluation are AE dates. Missing or incomplete AE dates are imputed according to BI standards (see BI-KMED-BDS-HTG-0035 (4)).

Missing data and outliers of PK data are handled according to BI standards (see BI-KMED-TMCP-MAN-0014) (5).

Missing baseline laboratory values will be imputed by the respective values from screening or from ambulatory visit (ptm -48:00) if available.

6.7 BASELINE, TIME WINDOWS AND CALCULATED VISITS

The baseline value is defined as the last measurement before first administration of Spesolimab (= value at V2 Day 1, in case no actual time is given in data).

The acceptable time windows for visits are given in the CTP Flow Chart and CTP Section 6.1.

Adherence to time windows will be checked via the consistency check listings at the RPM/DBLM.

Unscheduled measurements of laboratory data and vital signs data will be assumed to be repeat measurements of the most recent scheduled measurement (e.g. for follow-up or confirmation of a particular value). Therefore, unscheduled measurements will be assigned to the planned time point of the previous scheduled measurement.

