29	672:00	8:00		ambulatory visit	X	X	X		X	X	X ⁵
36	840:00	8:00		ambulatory visit	X						X
43	1008:00	8:00		ambulatory visit	X	X					X
57	1344:00	8:00		ambulatory visit	X	X					X ⁵
71	1680:00	8:00		ambulatory visit	X	X					X
92 ±2	2184:00	8:00		ambulatory visit	X	X	X ¹⁴				X
120 ±3	2856:00	8:00		ambulatory visit	X	X					X
148 ±3	3528:00	8:00		ambulatory visit	X	X					X
3	176 ±3	4200:00	8:00	EoTrial ¹²	X	X	X ¹⁴	X	X	X	X ⁵

Proprietary confidential information © 2021 Boehringer Ingelheim International GmbH or one or more of its affiliated companies

1. Screening with subject information, informed consent as the first measure, includes physical examination, check of vital signs including temperature, respiratory rate (RR), systolic and diastolic blood pressure (BP) and pulse rate (PR), 12-lead electrocardiogram (ECG), safety laboratory parameters (under fasting conditions), pregnancy test, drug screening, alcohol breath test, demographics (including determination of body height and weight, smoking and alcohol history), relevant medical history, concomitant therapy and review of inclusion/exclusion criteria.
2. The time is approximate; procedures are to be performed and completed within three hours prior to drug administration. Within three hours prior to the planned dosing, planned time -2:00 will be used.
3. Safety laboratory parameters include clinical chemistry, haematology, coagulation and urinalysis; in addition at screening: serology (hepatitis B virus [HBV], hepatitis C virus [HCV], human immunodeficiency virus [HIV], tuberculosis (QuantiFERON TB test), Follicle-stimulating hormone (FSH) and estradiol evaluation in questionable cases for determining postmenopausal status), and drug screening.
4. PK sampling times may be adapted based on information obtained during trial conduct.
5. Standardised assessment of local tolerability using the criteria swelling, induration, heat, redness, pain or other findings.
6. If several actions are indicated at the same time point, the intake of meals will be the last action.
7. Confirmation of fitness includes physical examination.
8. ADAs will be taken at baseline, Day 15, Day 29, Day 43, Day 57, Day 71, Day 92, Day 120, Day 148 and Day 176.
9. Only drug screening and alcohol breath test.
10. Evaluate vital signs at baseline, 10 minutes after and 1 hour post infusion/injection and in case of suspicion of hypersensitivity reaction including anaphylactic reaction.

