11. AEs and concomitant therapies will be recorded throughout the trial, but will be specifically asked for at the time points indicated in the Flow Chart above.
12. EoTrial (end of trial) examination includes physical examination, body weight, vital signs, 12-lead ECG, safety laboratory parameters, recording of AEs and concomitant therapies. EoTrial to be performed not before last PK and ADA sampling.
13. Safety laboratory parameters are to be taken within two days prior to trial medication administration under fasting conditions and can be omitted if the screening examination is performed between Day -5 and Day -3. Also the AEs and concomitant therapies will be queried on Day -1.
14. At these time points, a urine pregnancy test will be done for female subjects.

FLOW CHART I.V.

Single dose group for IV

Single dose of Spesolimab as 450 mg, 900 mg and 1200 mg IV. (Subjects will receive only one dose)

Visit	Day	Time relative to first drug administration (planned time) [h:min]	Approx. time (actual time) [h:min]	Event and comment	PK _{blood} ⁴	Plasma ADA ⁸	Laboratory ³	Body weight	12-lead ECG	Vital signs (BP, PR, RR, body temperature) ¹¹	Query on AEs, concomitant therapies ¹²
1	-28 to -3			screening ¹			X ¹⁵	X	X	X	
	-2	-48:00	8:00	ambulatory visit			X ¹⁴				X ¹⁴
2	-1	-12:00	20:00	admission to trial site			X ¹⁰				X
	1	-2:00	6:30		X ²	X ²	X ^{2,15}		X ²	X ²	X ^{2,5}
		0:00	8:00	drug administration start of infusion							
		0:10	8:10							X	
		0:30	8:30						X	X	X ⁵
		1:00	9:00							X	
		1:30	9:30	▼ end of infusion ⁹	X				X	X	
		2:00	10:00	light breakfast ⁶	X				X	X	
		3:00	11:00		X					X	
		4:00	12:00	lunch ⁶	X					X	X ⁵
		6:00	14:00						X	X	
		8:00	16:00		X					X	
		10:00	18:00	dinner ⁶							
		12:00	20:00		X				X	X	X ⁵
	2	24:00	8:00	breakfast ⁶	X				X	X	X ⁵
		28:00	12:00	lunch ⁶							
		32:00	16:00							X	
		34:00	18:00	dinner ⁶							X ⁵
	3	48:00	8:00	breakfast ⁶ discharge from trial site (confirmation of fitness) ⁷	X				X	X	X ⁵
	4	72:00	8:00	ambulatory visit	X		X				X ⁵
	5	96:00	8:00	ambulatory visit	X						X ⁵
	6	120:00	8:00	ambulatory visit	X						X ⁵
	7	144:00	8:00	ambulatory visit	X						X ⁵
	8	168:00	8:00	ambulatory visit	X		X		X	X	X ⁵
	15	336:00	8:00	ambulatory visit	X	X					X ⁵
	22	504:00	8:00	ambulatory visit	X		X		X	X	X
	29	672:00	8:00	ambulatory visit	X	X	X		X	X	X ⁵
	36	840:00	8:00	ambulatory visit	X						X
	43	1008:00	8:00	ambulatory visit	X	X					X
	57	1344:00	8:00	ambulatory visit	X	X					X ⁵

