5.2.3 Safety laboratory parameters

For the assessment of laboratory parameters, blood and urine samples will be collected by the trial site at the time points indicated in the Flow Chart after the subjects have fasted for at least 10 h. Overnight fasting is not required at the discretion of the investigator or designate for retests.

The parameters that to be determined are listed in [Tables 5.2.3: 1](#) and [5.2.3: 2](#). Reference ranges will be provided in the ISF.

Urine sediment examinations will only be performed if there is a clinically relevant abnormality in the urinalysis, and it is deemed clinically necessary by the investigator.

Proprietary confidential information © 2021 Boehringer Ingelheim International GmbH or one or more of its affiliated companies

Table 5.2.3: 1

Routine laboratory tests

Functional lab group	Test name
Haematology	Haematocrit Haemoglobin Red blood cell count (RBC) Reticulocyte count White blood cell count (WBC) Platelet count
Automatic WBC differential (relative and absolute cell count)	Neutrophils, eosinophils, basophils, monocytes, lymphocytes
Coagulation	Activated partial thromboplastin time (aPTT) Prothrombin time (Quick's test and INR) Fibrinogen
Enzymes	Aspartate transaminase (AST/GOT) Alanine transaminase (ALT/GPT) Alkaline phosphatase (ALP)) Gamma-glutamyl transferase (GGT) Creatine kinase (CK) CK-MB, only if CK is elevated Lactate dehydrogenase (LDH) Serum Immunoglobulin E (IgE) ¹
Hormones ²	Thyroid stimulating hormone (TSH) fT3, fT4
Substrates	Serum glucose Creatinine Total bilirubin Direct bilirubin Total protein Protein electrophoresis (Protein EP) ³ Albumin Globulin CRP Uric acid Total cholesterol Triglycerides
Electrolytes	Sodium Potassium Chloride Calcium Inorganic phosphate (IP)

Proprietary confidential information © 2021 Boehringer Ingelheim International GmbH or one or more of its affiliated companies

Table 5.2.3: 1 **Routine laboratory tests (cont.)**

Functional lab group	Test name
Urinalysis (Stix)	Urine nitrite Urine protein Urine glucose Urine ketone Urobilinogen Urine bilirubin Urine erythrocytes Urine leukocytes Urine pH
Urine sediment ⁴	Only positive findings will be reported (for instance, the presence of sediment bacteria, casts in sediment, squamous epithelial cells, erythrocytes, leukocytes)

1. In case of a potential systemic allergic reaction blood samples for determination of serum IgE will be collected 0.5 h, 2 h, 6 h and 24 h after onset of the event.
2. Only at screening

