5.2.6.1.4 Adverse events of special interest

The term AEs of special interest (AESI) relates to any specific AE that has been identified at the project level as being of particular concern for prospective safety monitoring and safety assessment within this trial, e.g. the potential for AEs based on knowledge from other compounds in the same class. AESIs need to be reported to the sponsor’s Pharmacovigilance Department within the same timeframe that applies to SAEs, please see [section 5.2.6.2.2](#).

The following are considered as AESIs in this trial:

- Hepatic injury, as defined by the following alterations of hepatic laboratory parameters:
 - an elevation of AST and/or ALT \geq 3-fold ULN combined with an elevation of total bilirubin \geq 2-fold ULN measured in the same blood sample, or
 - ALT, and/or AST elevations \geq 10-fold ULN

These lab findings constitute a hepatic injury alert and the subjects showing these lab abnormalities need to be followed up according to the ‘DILI checklist’ provided in the ISF. In case of clinical symptoms of hepatic injury (icterus, unexplained encephalopathy, unexplained coagulopathy, right upper quadrant abdominal pain, etc.) without lab results (ALT, AST, total bilirubin) available, the Investigator should make sure these parameters are analysed, if necessary in an unscheduled blood test. Should the results meet the criteria of hepatic injury alert, the procedures described in the DILI checklist should be followed.

- Systemic hypersensitivity including infusion reaction and anaphylactic reaction:
 - Any suspicion of severe infusion reaction systemic/hypersensitivity reaction and of any potential cases of anaphylaxis should be defined and assessed using the criteria discussed in the statement paper from Sampson HA ([Appendix 10.1.3, R11-4890](#)).
- Severe infections (according to RCTC grading in ISF)

Proprietary confidential information © 2021 Boehringer Ingelheim International GmbH or one or more of its affiliated companies

- Opportunistic and mycobacterium tuberculosis infections

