7.3.4 Safety analyses

Safety will be assessed for the endpoints listed in [section 2.1.2](#) and 2.2.2 based on the TS. Safety analyses will be descriptive in nature and will be based on BI standards. No hypothesis testing is planned. Treatments will be compared in a descriptive way. Tabulations of frequencies/proportions will be used for the evaluation of categorical (qualitative) data, and tabulations of descriptive statistics will be used to analyse continuous (quantitative) data.

Measurements (such as vital signs, or laboratory parameters) or AEs will be assigned to treatments (see [section 4.1](#)) based on the concept of treatment emergent AEs. Therefore,

Proprietary confidential information © 2021 Boehringer Ingelheim International GmbH or one or more of its affiliated companies

measurements planned or AEs recorded prior to intake of trial medication will be assigned to 'screening', those between trial medication intake and end of REP will be assigned to the treatment period. Events occurring after the REP but prior to trial termination date will be assigned to 'follow-up'. These assignments including the corresponding time intervals will be defined in detail in the TSAP. Note that AEs occurring after the last per protocol contact but entered before database lock will be reported to Pharmacovigilance only and will not be captured in the trial database.

Additionally, further treatment intervals (called analysing treatments) may be defined in the TSAP in order to provide summary statistics for other than above periods, such as combined treatments, on-treatment totals or periods without treatment effects (such as screening and post-trial intervals).

AEs will be coded using the Medical Dictionary for Regulatory Activities (MedDRA). Frequency, intensity and causal relationship of AEs will be tabulated by treatment, primary system organ class and preferred term. SAEs, AESIs (see [section 5.2.6.1.4](#)) and other significant AEs (according to ICH E3) will be listed separately.

Laboratory data will be compared to their reference ranges. Values outside the reference range will be highlighted in the listings. Additionally, differences from baseline will be evaluated.

Vital signs or other safety-relevant data observed at screening, baseline, during the course of the trial and at the end-of-trial examination will be assessed with regard to possible changes compared to findings before start of treatment.

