In Section 15.4 and Appendix 16.2 (Listings) of the CTR displays, the screening and follow-up period will be included and no totals will be provided.

Tables of vital signs and laboratory values will present results for the above mentioned on treatment phase.

For detailed information on the handling of the treatments refer to Technical TSAP ADS (analysis data set) plan and Analysis Data Reviewers guide.

6.2 **IMPORTANT PROTOCOL DEVIATIONS**

Data discrepancies and deviations from the CTP will be identified for all treated subjects.

Consistency check listings (for identification of deviations of time windows) and a list of protocol deviations (e.g. deviations in drug administration, in blood sampling times, etc.) will be provided to be discussed at the Report Planning Meeting and database lock meeting (RPM/DBLM). At this meeting, all manual deviations identified at the sites by the CRAs and deviations too complex to program will be reviewed by the trial team to decide which are considered important. For definition of important protocol deviations (iPD), and for the process of identification of these, refer to the Boehringer Ingelheim (BI) SOP "Identify and Manage Important Protocol Deviations (iPD)" (2).

If any iPDs are identified, they are to be summarised into categories and will be captured in the RPM/DBLM minutes via an accompanying Excel spreadsheet.

Categories which are considered to be iPDs in this trial were defined in the integrated quality and risk management plan (IQRMP) prior to trial initiation. The IPD list was transferred into the IPD specification file (due to changes in the SOP) (3). Within this transfer some minor adaptations were done to comply with new naming conventions and categorisations. IPDs will be identified no later than in the Report Planning Meeting and the IPD categories will be updated as needed. The decision on exclusion of subjects from analysis sets will be made after discussion of exceptional cases and implications for analyses.

The iPDs will be summarised and listed.

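### SAP 6.7 gives an unscheduled lab drawn between dosing and the 72:00 sample a pre-dose planned time, and the documents do not settle which study phase it then belongs to

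*SAP*

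**What the plan says.** SAP 6.7 sets the rule and its scope: "Unscheduled measurements of laboratory data and vital signs data will be assumed to be repeat measurements of the most recent scheduled measurement". It concludes: "Therefore, unscheduled measurements will be assigned to the planned time point of the previous scheduled measurement". The reason it gives is that such values follow up or confirm an earlier one.

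The same section defines baseline as the last measurement before first administration, with the Visit 2 Day 1 value as the fallback where no actual time is recorded. SAP 7.8.2 repeats the pre-dose definition for all laboratory outputs.

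Two places deal with study phase:
- Protocol 7.3.4: "measurements planned or AEs recorded prior to intake of trial medication will be assigned to" screening. Those between intake and the end of the residual effect period go to the treatment period, and the details are left to the SAP.
- SAP 6.1 starts the on-treatment phase at the time of administration or start of infusion. It introduces these phases for the analysis of AEs, then adds: "Tables of vital signs and laboratory values will present results for the above mentioned on treatment phase".

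The protocol foresees event-driven labs. Footnote 1 of Table 5.2.3:1 covers a suspected systemic allergy: "blood samples for determination of serum IgE will be collected 0.5 h, 2 h, 6 h and 24 h after onset of the event". Under Protocol 5.2.6.1.4, symptoms of hepatic injury without liver results call for testing, "if necessary in an unscheduled blood test".

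**The concern.** A repeat rule is harmless when the scheduled value and its repeat lie on the same side of dosing. Here they may not. A lab prompted by an event during the infusion or the 48-hour in-house stay is new post-dose information, yet it takes the label of the sample drawn before dosing.

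The label matters if it also decides the phase. SAP 7.8.2 gives on-treatment minimum and maximum values, counts of possibly clinically significant abnormalities, AST/ALT counts by multiples of ULN, and an eDISH plot for the on-treatment period. An abnormal value moved to screening would be absent from whichever of these are restricted to the on-treatment phase, and they would then look cleaner than the data.

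**Working it through.** The plan states no figure to reproduce. The check applies the SAP 6.7 rule to the scheduled times.

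**Inputs.** Safety-lab times are the same in both flow charts, in hours from dosing and apart from screening: -48, -2, 72, 168, 504, 672, 2184, 4200. For the pre-dose sample, footnote 2 says: "Within three hours prior to the planned dosing, planned time -2:00 will be used". The Day -1 laboratory mark is limited to drug screening and the alcohol breath test. The first post-dose vital signs are at 0:10.

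**Rule.** Assigned time = the latest scheduled time not after the actual time t.

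**Labs.**
- t = 0.05, 0.5, 2, 6, 24, 48 and 71.9 h: all assigned to -2:00.
- t = 72.5 and 100 h: assigned to 72:00.
- Gap between scheduled labs: 72 - (-2) = 74 h, of which 72 h is after dosing.

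**IgE series** (onset + 0.5, 2, 6 and 24 h), if the rule is applied at visit level. All four samples take -2:00 when onset + 24 < 72, that is, when onset is before 48 h.
- Onset 0.25 h: samples at 0.75, 2.25, 6.25 and 24.25 h, all assigned to -2:00.
- Onset 47 h: samples at 47.5, 49, 53 and 71 h, all assigned to -2:00.
- Onset 60 h: samples at 60.5, 62 and 66 h assigned to -2:00; the one at 84 h assigned to 72:00.

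**Vital signs.** Only 0 < t < 10 minutes maps to -2:00; at t = 0.5 h the assigned time is already 0:30. SAP 7.8.3 summarises the last value assigned to a planned time, so a repeat in those 10 minutes would displace the true pre-dose value in any -2:00 row.

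**Baseline.** Every t > 0 is after administration, so a value with a recorded time cannot be the last one before it. Only a post-dose value with no recorded time, carrying the Visit 2 Day 1 label, could meet the fallback.

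**Phase.** On-treatment by actual time runs from dosing to 16 weeks = 16 × 7 × 24 = 2688 h after administration or end of infusion. Every re-labelled lab lies inside it.

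| Time that sets the phase | Source | Phase of a lab at 6 h | On-treatment displays |
|---|---|---|---|
| Planned (-2:00) | Protocol 7.3.4 | Screening | Value lost |
| Actual (6 h) | SAP 6.1 | On treatment | Value kept, with a pre-dose visit label |

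Neither document says which row applies. SAP section 4, which lists departures from the protocol, does not mention the point.

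**The case against.** A reader might infer that early abnormalities will be reported as baseline or screening values. The documents do not support that as a stated outcome. The baseline part is contradicted by SAP 6.7 and 7.8.2. Protocol 6.1 also requires exact times to be documented for measurements outside the permitted windows, so untimed post-dose labs are not to be expected. The screening part depends on one reading: Protocol 7.3.4 also sends measurements between intake and the end of the residual effect period to the treatment period, and SAP 6.1 can be read as carrying its actual-time phases over to the lab tables.

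Other points on the plan's side also stand:
- SAP 7.8.2 leaves repeat values to a sponsor guidance, and SAP 6.1 leaves treatment handling to a technical data-set plan. Neither is available here, and either might resolve the matter.
- With no scheduled lab between -2:00 and 72:00, a by-visit table has no correct row from which the value goes missing.
- Table 5.2.3:1 ties IgE to an event. If IgE is not measured at -2:00, there is no scheduled IgE value to repeat, and the rule may not reach that series.
- Investigator-judged relevant findings become AEs, hepatic injury and systemic hypersensitivity are AEs of special interest with their own table, and all individual values are listed.

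These points limit the consequences but do not remove the rule. The AE route depends on the investigator's judgement; the rule-based abnormality, xULN and eDISH displays do not, and they are the outputs exposed.

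**Conclusion.** The labelling fault is certain on the text: SAP 6.7 gives any unscheduled lab after dosing and before the 72:00 sample a pre-dose planned time. For vital signs the window is 10 minutes and minor.

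Loss from the on-treatment displays is conditional on planned time setting the phase, which the documents leave open. So is any claim that the lab safety profile is biased towards looking cleaner. The documents give no basis for estimating how many such labs will occur. As a scale only, one subject wrongly left out of a count in a group of 10 moves that rate by 1/10 = 10 percentage points.

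All these analyses are descriptive, and no primary endpoint is touched. The point still deserves correction, because a written rule moves values across the dosing boundary and the repair is small.

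**What to change.** Add to SAP 6.7:
- A measurement taken after the start of dosing is never assigned to a pre-dose planned time point and never used as baseline.
- Its study phase is set by actual date and time.
- Unscheduled values after dosing and before the first scheduled post-dose assessment are labelled as unscheduled post-dose. They count in the on-treatment minimum and maximum, possibly-clinically-significant, xULN and eDISH outputs.

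The wording should cover laboratory data and vital signs alike. The cost is a short SAP addition and a small change to the analysis-dataset derivation, with no new data or procedures.
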